16.0 Statistical Considerations and Methodology

16.1 Overview:

This study is a phase II screening study. It is divided into two portions. The safety portion is designed to determine the dose of the treatment agents. The expansion portion is designed to continue enrollment at the acceptable dose levels to determine efficacy of treatment in elderly (age 60+) newly diagnosed AML patients (Arm A: AZD1775 days 1-5 & 8-12) and AraC days 1-5 & 8-12) and to make a selection of one of the two randomized arms for Relapsed/Refractory AML and HMA failure MDS patients (Arm B: AZD1775 days 1-5 & 8-12) and AraC days 1-5 & 8-12; Arm C: AZD1775 days 1-5, 8-12, 15-19, 22-26).

The purpose of this screening design is NOT TO ensure a high probability that the very best treatment is selected, but to ensure a low probability that a poor treatment is selected. In other words, at the conclusion of this trial, we cannot make a definitive conclusion about the superiority of one treatment compared to the other, but we can ensure that there is a small probability of bringing the inferior treatment forward.

- 16.2 Statistical Design and Analysis for the Primary Endpoint
 - 16.21 Primary Endpoint

The primary endpoint of this trial is the rate of complete response (CR plus CRi). Throughout Section 16.0, complete response will be considered synonymous with "success", unless specified otherwise. All patients meeting the eligibility criteria, who have signed a consent form, and have begun treatment at the study MTD will be evaluable for complete response, with the exception of patients who are determined to be a major treatment violation.

Treatment Responses will be assessed by standard criteria for the respective disease per NCCN guidelines or according to specific criteria from expert panels (i.e. the International Working Group Criteria for the response in acute myeloid leukemias). Response will be assessed by peripheral blood criteria at the end of each cycle and every other cycle (for MDS) thereafter (Burnett et al. 2007. Gileset al. 2005, Kantarijian et al. 2012, Fenaux et al. 2009). Bone marrow tests to assess responses will be carried as outlined in the study tables

Bone marrow tests to assess responses will be carried as outlined in the study tables Table 4.1 and 4.2.

16.22 Arm A: Efficacy and safety of AZD1775 + AraC in elderly newly diagnosed AML

Statistical Design, Analysis and Decision Rule

Efficacy and safety of AZD1775 + AraC will be tested in elderly patients with newly diagnosed AML using a single-arm single-stage binomial design. The primary endpoint will be the complete response rate, which will be defined as an objective status of CR or CRi. Complete response rate will be evaluated over all cycles of study treatment. The proportion of CR/CRi responses will be estimated by the number of CR/CRi responses divided by the total number of evaluable patients. Two-sided 95% confidence intervals will be computed using an exact binomial confidence interval. The frequency and relative frequency of individual response categories will also be computed. For a subject to be considered evaluable for statistical analysis, the subject must be eligible, provide consent, initiate treatment and not experience a major treatment violation during the first cycle of treatment.

The largest CR/CRi response proportion where the proposed treatment regimen would be considered ineffective in this population is 15% (Burnett et al. 2007. Gileset al. 2005, Kantarijian et al. 2012, Fenaux et al. 2009) and the smallest CR/CRi response proportion that would warrant subsequent studies with the proposed regimen in this patient population is 40%.

The following one-stage binomial design uses 21 patients to test the null hypothesis that the true CR/CRi response proportion in a given patient population is at most 15%.

Decision Rule: Enter 21 patients into the study. If 5 or fewer CR/CRi responses are observed in the first 21 evaluable patients, we will consider this regimen ineffective in this patient population. Otherwise, if 6 or more CR/CRi responses are observed in the first 21 evaluable patients, we may recommend further testing of this regimen in subsequent studies in this population. We anticipate accruing an additional 2 patients to account for ineligibility, cancellation, major treatment violation, or other reasons. Thus, the total maximum accrual to this arm is 23 patients.

Assuming that the number of CR/CRi responses is binomially distributed, the significance level within this arm is </=10% and the probability of declaring that this regimen warrants further studies (i.e., statistical power) under various CR/CRi response proportions can be tabulated as a function of the true CR/CRi response rate as shown in the following table.

If the true CR/CRi rate is	0.15	0.20	0.25	0.30	0.35	0.40
Then the probability of declaring that the regimen warrants further studies is	0.08	0.23	0.43	0.64	0.80	0.90

16.23 Arm B and C: Efficacy and safety of AZD1775 in combination with AraC compared to AZD1775 alone in relapsed/refractory AML or HMA failure MDS patients.

Statistical Design, Analysis and Decision Rule

Efficacy and safety of AZD1775 alone or with AraC will be tested in patients with relapsed/refractory AML and patients with HMA failure MDS using a flexible randomized phase II selection design. Patients will be randomized to AZD1775 alone or with AraC in a 1:1 fashion using a dynamic allocation procedure (Pocock & Simon 1975). The primary endpoint will be the complete response rate, which will be defined as an objective status of CR or CRi. Complete response rate will be evaluated over all cycles of study treatment. The proportion of CR/CRi responses will be estimated by the number of CR/CRi responses divided by the total number of evaluable patients (by arm). Two-sided 95% confidence intervals will be computed using an exact binomial confidence interval. The frequency and relative frequency of individual response categories will also be computed. Estimates will also be computed by arm separately for each disease. For a subject to be considered evaluable for statistical analysis, the subject must be eligible, provide consent, initiate treatment and not experience a major treatment violation during the first cycle of treatment.

The selected design is a flexible randomized phase II selection design (Sargent & Goldberg 2001). This study will randomize 40 evaluable patients (20 per arm). The minimum required number of CR/CRi responses for an arm to be considered as having evidence of efficacy is 3 (out of 20 evaluable patients). This decision rule is based on a single-arm single-stage binomial design testing the null hypothesis that the true CR/CRi response proportion in a given arm is at most 5% (Tawfik et al. 2014, Giles et al. 2005, Jabour et al. 2010, Prevet et al. 2011) with the smallest CR/CRi response proportion warranting subsequent studies being 25%.

In the event that both arms meet this decision rule for efficacy, the combination arm will be considered as having additional efficacy over the single-agent arm if the CR/CRi response rate on the combination arm is at least 10% greater than the single-agent arm. If the difference is <10%, then the trial is considered statistically ambiguous and the selection between the combination and single-agent arm will be allowed to include other factors (e.g., adverse event data) in addition to the CR/CRi response rate. We anticipate accruing an additional 4 patients (2 patients per arm) to account for ineligibility, cancellation, major treatment violation, or other reasons. Thus, the total maximum accrual to Arm B is 22 patients and to Arm C is 22 patients.

Assuming that the number of CR/CRi responses is binomially distributed, the significance level for the single-arm decision rule requiring a minimum of 3 (out of 20 evaluable patients) within an arm is </=10% and the probability of declaring that a given arm's treatment regimen warrants further studies (i.e., statistical power) under various CR/CRi response proportions can be tabulated as a function of the true CR/CRi response rate as shown in the following table.

If the true CR/CRi rate is	0.05	0.10	0.15	0.20	0.25
Then the probability of declaring that a given arm's treatment regimen warrants further studies is	0.08	0.32	0.60	0.79	0.91

Probabilities for the combination arm being selected as the overall winner are provided in the following table.

CR/CRi rate	CR/CRi rate	Probability combo selected over
(AZD1775 alone)	(AZD1775 + AraC)	single-agent arm
0.05	0.05	0.07
0.25	0.25	0.30
0.20	0.25	0.44
0.15	0.25	0.61
0.10	0.25	0.77
0.05	0.25	0.88

16.3 Sample Size, Accrual Rate, and Study Duration

This design is expected to accrue 18 patients to the safety portion with the possibility of enrolling up to 54. Six patients in each of the safety arms will be treated at the MTD and thus will be eligible for primary endpoint analysis. An additional 15 patients in Arm A and 14 patients in both arm B and C will be enrolled per treatment arm in the expansion portion with the addition of another 2 per arm to account for ineligibility, cancellation, major treatment violation, or other reasons. Thus the final accrual may be as large as 102 or as low as 67 (Arm A: 23; Arm B: 22; Arm C: 22).

The anticipated accrual rate is 4-6 evaluable patients per month. Therefore, the accrual period is expected to be approximately 1.5-2 years. The primary endpoint will be evaluated approximately 2.5 years after the trial opens, or after the last patient accrued has been observed for at least 4 months. The total study duration is expected to be approximately 2.5 years.

16.4 Secondary Endpoints

- 16.41 Safety and tolerability data will be compiled. The maximum grade for each type of adverse event will be recorded for each patient, and frequency tables will be reviewed to determine patterns (by arm, disease and overall). Additionally, the relationship of the adverse event(s) to the study treatment will be taken into consideration. The rate of grade 3 or higher non-hematologic adverse events, and the rate of grade 4 or higher adverse event (hematologic and non-hematologic) will be computed each with a 95% exact binomial confidence interval.
- 16.42 Summary statistics for clinical benefit (mean and standard deviations for continuous variables and frequencies and percentages for discrete variables) will be compiled for hematologic improvements and transfusion requirements.

- 16.43 Duration of response is defined for all evaluable patients who have achieved a response as the date at which the patient's earliest best objective status is first noted to be a CR/CRi response to the earliest date progression is documented. If a patient dies subsequent to the response without a documentation of disease progression, the patient will be censored at the last date disease was assessed. In the case of a patient failing to return for evaluations before a documentation of disease progression, the patient will be censored for progression on the date of last evaluation. The distribution of duration of response will be estimated using the method of Kaplan-Meier (1958).
- 16.44 Time to response/progression is defined as the time from registration to the earliest date of documentation of response/disease progression. If a patient dies without a documentation of disease progression the patient will censored at the last date disease was assessed. In the case of a patient starting treatment and then never returning for any evaluations, the patient will be censored for progression 1 day post-registration. The distribution of time to progression will be estimated using the method of Kaplan-Meier (1958).
- 16.45 Survival time is defined as the time from registration to death due to any cause. The distribution of survival time will be estimated using the method of Kaplan-Meier (1958).
- 16.46 Time to AML or death is defined for all evaluable patients with MDS as the time from registration to leukemic transformation or death due to any cause. The distribution of time to AML or death will be estimated using the method of Kaplan-Meier (1958).
- 16.5 Exploratory Analysis

An exploratory analysis will be conducted, if there is indication, to determine any differences in study endpoints for subgroups of patients within each treatment arm as defined by the grouping factors (section 5.0), descriptive factors (section 12.0), dose level or any other patient demographics.

- 16.6 Correlative Research
 - 16.61 Statistical analysis of pharmacokinetics and biomarkers will be primarily descriptive. Continuous biomarker levels will be explored in a graphical manner including mean plots and plots of change and percent change from baseline and other summary measures. Any potential relationships between the baseline level or change in the level of each biomarker and clinical outcome such as overall response, 6-month progression and survival, and adverse event incidence will be further analyzed using Wilcoxon rank sum tests or logistic regression methods, as appropriate. Association between a dichotomized biomarker and overall response will be assessed using a chi-squared test. Comparisons with 1-sided p-values ≤0.10 are considered significant. As this correlative component is exploratory in nature, we have not adjusted for multiple comparisons.
 - 16.62 Patient-reported outcomes will be assessed at baseline and at the end of each cycle of treatment. MPN-SAF TSS was created to address the constellation of

symptoms. The MPN-SAF includes 1 item measuring fatigue from the previously validated Brief Fatigue Inventory (BFI), as well as linear analog scales capturing early satiety, abdominal discomfort, inactivity, concentration problems, numbness/tingling in the hands/feet, night sweats, itching, bone pain, fever, and weight loss. The MPN-SAF TSS has previously been validated for use at a single time point by co-administration with previously validated instruments.

Ouality of life will be assessed prior to review of treatment response and discussions of patient's general health since last treatment evaluation. QOL will be measured using the EORTC QLQ-C30, a 30-item patient-reported guestionnaire about patient ability to function, symptoms related to the cancer and its treatment, overall health and guality of life, and perceived financial impact of the cancer and its treatment. 28 of the 30 items are measured on a 1-4 scale (1=not at all; 4=very much) with the remaining two items (overall health and overall quality of life) scored on a 1-7 numeric analogue scale (1=very poor; 7=excellent). The recall period for the EORTC QLQ-C30 is one week. The EORTC QLQ-C30 is the product of more than a decade of collaborative research and to date, more than 2200 studies using the EORTC QLQ-C30 have been registered with the EORTC (Fayers et al, 2001 [EORTC Scoring Manual]). The patient booklet containing this questionnaire will be administered to all willing patients via a paper booklet in clinic at baseline and on day 1 of every cycle starting with Cycle 2, and will be scored according to the published scoring algorithms.

Scale score trajectories over time and changes from baseline over time will be examined using repeated measures or growth curve models, as appropriate, stream plots and mean plots with standard deviation error bars overall. Scores and changes at each cycle will be statistically tested using paired t-tests, and standardized response means (i.e. effect sizes) (mean of the change from baseline scores at a given cycle, divided by the standard deviation of the change scores) will be interpreted (after applying Middel's (2002) adjustment) using Cohen's (1988) cut-offs: <0.20 = trivial; 0.20-<0.50 = small; 0.50-<0.80 = moderate; and >=/0.80 = large.

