1.0 Background

1.1 Acute Myeloid Leukemias (AML) and Myelodysplastic Syndrome (MDS)

Despite progress in the treatment of AML and MDS, most adult patients with AML and advanced/progressive MDS still do very poorly with current therapy and many die from their disease (Abe et al. 2008). Patients with primary refractory or relapsed AML have a particularly poor outcome, as well as MDS patients who are refractory, progress on or relapse after hypomethylating agents (HMA) based therapies (Duong et al. 2013, Prébet et al. 2011, Jabbour et al. 2010).

Acute myeloid leukemia patients who fail to achieve a complete remission (CR) with first induction therapy have a dismal outcome and only a small percentage of patients are alive at 1 year (Bai et al 2008). Current therapy is also inadequate for relapsed leukemias with a true long-term cure rate of less than 10% (Bai et al. 2008). Recently, comparable clinical activity and outcomes between HMAs and cytotoxic chemotherapy has been demonstrated in secondary, elderly and unfavorable cytogenetics AML in first line therapy (Quantas-Cardama et al. 2012 and Fenaux et al. 2010). Thus, many experts feel that these patients are candidates for lower intensity treatment as first line intervention.

The outcome of patients with advanced myelodysplastic syndrome (MDS) in the intermediate and IPSS intermediate-2, and especially high-risk category is almost as poor as for patients with acute leukemia. Median survival in this group is 4-5 months (Schanz et al. 2012 and Greenberg et al. 1997). The two approved HMAs Azacytidine (AZA) and Decitabine (DAC) have activity, however CR rates are less than <10-18% and overall responses (CR, PR and clinical benefit such as hematological improvements) approach at a maximum 40-50% in the first line treatment setting in MDS (Fenaux et al 2009 and Lubbert et al 2011).

Responses and survival in MDS patients having failed or progressed on or after HMA treatment is very poor with a median survival of 4.3-5.8 months and a 1-year survival of 17-29% in the largest three studies to date (Duong et al. 2013, Prébet et al. 2011, Jabbour et al. 2010). Accordingly HMA failure MDS represents one of the largest patient groups in need for novel agents and investigational therapies. In fact, apart from allogeneic transplant for which most patients do not qualify, investigational regimens were as good and better than cytotoxic chemotherapy after HMA failure (Prébet et al. 2011).

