2.0 Goals

2.1 Primary Goals

- 2.11 To estimate the clinical efficacy of AZD1775 in combination with AraC in patients with newly diagnosed AML by assessing complete response (CR plus CRi) rates
- 2.12 To estimate the clinical efficacy of AZD1775 alone or in combination with AraC in patients with relapsed/refractory AML and hypomethylating agent failure MDS by assessing complete response (CR plus CRi) rates
- 2.2 Secondary Goals
 - 2.21 To determine the safety and tolerability of AZD1775 alone or combined with AraC in the study population.
 - 2.22 To estimate additional measures of clinical benefit (i.e. hematological improvements, transfusion requirements).
 - 2.23 To measure the duration of response of AZD1775 alone or combined with AraC.
 - 2.24 To measure time to response of AZD1775 alone or combined with AraC.
 - 2.25 To measure time to progression of AZD1775 alone or combined with AraC.
 - 2.26 To measure overall survival of AZD1775 alone or combined with AraC.
 - 2.27 To measure time to AML (for MDS subjects) of AZD1775 alone or combined with AraC
- 2.3 Correlative Research
 - 2.31 To determine the pharmacokinetics (PK) of AZD1775 alone or combined with AraC in the study population
 - 2.32 To conduct correlative research studies characterizing underlying molecular events and solidifying putative mechanism of action in vivo and to identify potential pharmacodynamic/biomarkers of response to AZD1775 alone or combined with AraC
 - 2.33 To evaluate quality of life (QOL) and patient-reported symptoms in subjects treated with AZD1775 alone or combined with AraC.

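### Goal 2.27 is time to AML in MDS patients, but the only planned analysis (16.46) is AML or death, so transformation itself is never estimated

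*Combined protocol and SAP*

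**What the plan says.** Section 2.2 (Secondary Goals) lists goal 2.27: "To measure time to AML (for MDS subjects) of AZD1775 alone or combined with AraC". Death is not part of the goal.

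Section 16.46 supplies the endpoint: "Time to AML or death is defined for all evaluable patients with MDS". The clock starts at registration, the event is whichever comes first of transformation to leukemia and death from any cause, and the distribution is estimated by Kaplan-Meier.

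Section 16.45 handles overall survival separately: "Survival time is defined as the time from registration to death due to any cause".

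For the expected course of MDS after hypomethylating-agent (HMA) failure, section 1.1 cites "a median survival of 4.3-5.8 months and a 1-year survival of 17-29" per cent.

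**The concern.** Goals 2.23 to 2.26 (duration of response, time to response, time to progression, overall survival) each have an endpoint of the same name in 16.43 to 16.45. Goal 2.27 is the only time-to-event goal whose endpoint gains a second type of event.

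In a population with high mortality, the added event can carry much of the curve. The planned output would then be compatible with quite different rates of transformation, and a reader looking for the answer to goal 2.27 would not find it. Section 16.9a says that secondary endpoints will be posted publicly, so a composite reported against a time-to-AML goal could be misread.

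**Working it through.** **1. Does any other planned analysis isolate transformation?**

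| Section | What it estimates | Isolates AML? |
|---|---|---|
| 16.44 | Time to progression | No. In 11.2, MDS progression also includes falls in counts or hemoglobin and renewed transfusion dependence |
| 16.45 | Death from any cause | No |
| 16.46 | First of AML or death | No |
| 16.5 | Subgroup differences in existing endpoints | No |

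No section plans a cumulative incidence of AML or a count of first events by type. The documents give no event count or rate for this endpoint, so there is no planned figure to reproduce.

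**2. A bound that needs no transformation rate.** Every patient who has died by 12 months has had a composite event by then, either as death without AML or as an earlier transformation. So

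P(AML or death by 12 months) ≥ P(death by 12 months) = 1 − S(12).

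With S(12) = 0.29 the bound is 0.71. With S(12) = 0.17 it is 0.83. The composite is therefore at least 71-83% even if no patient transforms.

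**3. What the composite and survival curves give together.** The composite minus the death probability is the proportion alive after transformation. That is only a lower bound on AML incidence, because patients who transformed and then died are not in it. At 12 months it cannot exceed S(12), that is 17-29%. The cumulative incidence of AML could lie anywhere from that difference up to the composite itself.

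**4. Illustration under assumptions.** Take constant hazards: h1 for AML, h2 for death without AML, h3 for death after AML. Let a = h1 + h2, and let s = h1/a be the AML share of first events. Then

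- overall survival: S(t) = exp(−at) + [h1/(h3 − a)]·[exp(−at) − exp(−h3·t)]
- composite by 12 months: 1 − exp(−12a)
- cumulative incidence of AML: s·[1 − exp(−12a)]
- Kaplan-Meier for AML with deaths censored: 1 − exp(−12sa)

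The value of a is set so that median survival is 4.3 or 5.8 months (section 1.1). The share s and the median survival after AML (2 or 4 months) are assumptions, because the documents give neither. For example, with a survival median of 5.8 months, 2 months after AML and s = 0.3, the composite median is 4.85 months and a = 0.693/4.85 = 0.143. The composite is 1 − exp(−1.715) = 0.82, the AML incidence 0.3 × 0.82 = 0.246, and the death-censored figure 1 − exp(−0.515) = 0.402.

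| Assumed AML share | 12-month composite | 12-month AML incidence | Deaths censored |
|---|---|---|---|
| 10% | 78-88% | 8-9% | 14-19% |
| 30% | 82-94% | 25-28% | 40-56% |
| 60% | 88-99% | 53-59% | 72-94% |

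Modelled 1-year survival in these rows is 9-23%, somewhat below the cited 17-29%, so the table shows a pattern and is not a forecast. With the 5.8-month median and 2 months after AML, the composite moves only from 78% to 88% while AML incidence moves from 8% to 53%. Censoring deaths is not a repair: it overstates AML incidence in every row.

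**The case against.** The best defence is that 16.46 names its endpoint correctly each time and nowhere calls the curve time to AML. The composite is a recognised endpoint, includes every transformation that is a first event, and avoids treating deaths as uninformative censoring. Goal 2.27 can be read as shorthand for it, and rewording the goal would remove the mismatch with no new analysis. All of that stands, except that rewording gives up the stated goal instead of answering it.

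The defence is also right about two stronger readings that a reader might infer.

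- **That the composite is mostly death.** Section 1.1 gives total mortality, not the split of first events. A patient who transforms and then dies counts as an AML event. Over assumed AML shares of 10-70%, death without AML is 90-30% of first events, so the documents do not settle it.
- **That the composite overstates transformation by some multiple, such as 2-5 times.** Under proportional hazards that ratio is just the reciprocal of the assumed share (1/0.5 to 1/0.2). Nor can the cited survival median serve as the composite median, since the composite comes earlier whenever a patient transforms first.

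The cited survival figures also may not carry over. Section 3.12 admits any MDS after HMA failure or intolerance, and allows CMML and MDS/MPN overlap.

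Finally, complete AML data cannot be taken for granted. Section 11.2 does not define leukemic transformation, and its progression bands run to 20-30% blasts, so passing 20% is not itself marked as AML. After cycle 4, MDS marrows are largely at physician discretion (Table 4.2). Patients with progression move to event monitoring (13.2), and the follow-up schedule in section 18 lists progression, death and new primary but no AML entry. This limits any AML-specific estimate, and to a lesser degree 16.46 itself.

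**Conclusion.** The mismatch holds on the text alone: goal 2.27 asks for time to AML, and the one matching analysis estimates AML-free survival. The planned output cannot recover the incidence of transformation.

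The only size that follows from the documents is the bound of 71-83% for the 12-month composite, and it rests on the cited 1-year survival applying to the enrolled MDS patients. The table above is illustrative.

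The consequence is small. The endpoint is secondary and descriptive, with no test or decision rule. The MDS patients are an unspecified part of the 40 evaluable patients in Arms B and C (16.23), and the primary analysis is unaffected. This is a cheap improvement.

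**What to change.** - Keep 16.46 as it is defined, and label it AML-free survival.
- Add, as the analysis of goal 2.27, a table of first events by type and arm (AML, death without AML, neither) and the Aalen-Johansen cumulative incidence of AML by arm, with death without AML as a competing event. State that Kaplan-Meier with deaths censored will not be used for this.
- Write one definition of leukemic transformation and one censoring rule, and use both for 16.46 and the new estimate. 16.46 states neither at present.
- Add AML transformation and its date to the event-monitoring form, so that transformations after treatment ends are captured.

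**Cost.** One more estimate and one form field. The transformation and death dates are those that 16.46 already needs. The downsides are wide intervals in a small MDS subset and some dependence on how fully AML is ascertained once patients leave treatment. If the team does not want the extra estimate, the minimum is to reword goal 2.27 as AML-free survival.
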